5.1.5 Planned Study Calendar

The following dates are approximate. The actual dates may differ as, for example, the study will not start until all the appropriate regulatory and ethical approvals have been obtained.

Planned study period – FVFS (first Visit, first subject) to LCLS (last contact, last subject): November 2019 to March 2022

Planned inclusion period – FVFS to FVLS (first visit, last subject): November 2019 to September 2020

Planned vaccination period: November 2019 to September 2021

Planned end of study: March 2022

Planned date of final clinical study report: Q4 2022

5.1.6 Early Safety Data Review

The safety of the CYD dengue vaccine will be continuously monitored by the Sponsor. In the context of this study (ie, HIV-positive adults), a blinded ESDR will be performed, the goal of which is to allow for a cautious, stepwise approach to vaccine administration. An initial safety review for this study is planned when the first 20 subjects have received the first injection and have provided safety data for Days 0-14 post-injection 1. During the ESDR, study recruitment (and second injection for first 20 subjects, in case the safety review has not been completed at the time of second injection) will be paused.

The safety data collected will be entered into the CRF, and will be summarized, and reviewed by the Sponsor. The SET will review the blinded and unclean data and prepare a recommendation that will be reviewed by the IDMC. The IDMC will also review the safety data and then provide recommendation as to whether vaccination of the first enrollees and the enrollment of remaining subjects should resume or not. The ESDR will be assessing the following safety parameters:

- Immediate (within 30 minutes) AEs
- Solicited injection site and systemic reactions
- Unsolicited AEs reported as related by the Investigator within 14 days after the first injection
- SAEs and AESIs (including serious and non-serious AESIs)

Case unblinding may be performed if required. Moreover, some unblinded analyses may be provided by an independent Sanofi Pasteur statistician (ie, not involved either in the study or in the Dengue project) upon IDMC request.

The decision regarding the continuation of vaccination of the 20 first enrollees and the enrollment of the remaining 130 subjects will be communicated to the Investigators and will be sent to the involved IECs/IRBs and to the IDMC for information.

5.2 Enrollment and Retention of Study Population

5.2.1 Recruitment Procedures

Before the start of the study, Investigators and/or study staff will prepare a pre-screening data log listing eligible participants identified at least 4 weeks before the site begins recruitment. Using the most appropriate methods they will contact a pool of potential subjects and invite them to

participate in the study. Each site will ensure that all advertisements or materials planned to be used to recruit subjects (eg, letters, pamphlets, posters) are submitted to Sanofi Pasteur for review prior to submission to the IEC/IRB for approval.

Enrollment will begin once the first site enrolls the first subject into CYD50. A review of the enrollment at each site will be made by the Sponsor on a monthly basis with the aim of identifying potential issues with the completion of enrollment within the planned timelines. Should the Sponsor consider that a site is at risk of not meeting its expected target enrollment (ie, 50 subjects), this will be discussed with the site. If, after this discussion, there remains a risk to completion, Sanofi Pasteur reserves the right to re-allocate subject recruitment target from this site to another site.

5.2.2 Informed Consent Procedures

Informed consent is the process by which a subject voluntarily confirms his or her willingness to participate in a particular study. Informed consent must be obtained before any study procedures are performed. The process is documented by means of a written, signed, and dated ICF.

In accordance with GCP, prior to signing, and dating the consent form, the subject must be informed by appropriate study personnel about all aspects of the study that are relevant to making the decision to participate, and must have sufficient time and opportunity to ask any questions.

If the subject is not able to read and sign the ICF, then it must be signed and dated by an impartial witness who is independent of the Investigator. A witness who signs and dates the consent form is certifying that the information in this form and any other written information had been accurately explained to and understood by the subject or his / her guardian / representative.

The actual ICF used at each center may differ, depending on local regulations and IEC / IRB requirements. However, all versions must contain the standard information found in the sample ICF provided by the Sponsor. Any change to the content of the ICF must be approved by the Sponsor and the IEC / IRB prior to the form being used.

If new information becomes available that may be relevant to the subject's willingness to continue participation in the study, this will be communicated to him / her in a timely manner. Such information will be provided via a revised ICF or an addendum to the original ICF.

ICFs will be provided in duplicate of the signed consent will be made. The original will be kept by the Investigator, and the copy will be kept by the subject.

Documentation of the consent process should be recorded in the source documents.

5.2.3 Screening Criteria

The Screening Visit will take place within 4 weeks before the first injection. After a potential participant has signed an IEC/IRB-approved ICF, she/he will have a blood sample drawn in order to be screened for previous exposure to dengue, HBsAg, HCV antibodies^a, and for any hematological (hemoglobin, hematocrit, platelet count, white blood cells count) or biochemical (aspartate aminotransferase, alanine aminotransferase, urea, and creatinine) abnormalities. If

^a Unless documented information on previous infections is already available at the time of screening.

serology, hematology, and biochemistry results are available and were obtained within 4 weeks before first injection, tests do not need to be performed again.

Pre-injection HIV viral load and CD4 count will come from routine periodical tests of subjects as per local guidelines. For subjects for whom HIV viral load and CD4 count have not been assessed within 2 months before the Screening Visit, the Investigator will perform tests to ensure that results are available at the time of Visit 1.

Subjects' previous exposure to dengue will be assessed using a RDT (*OnSite*TM Dengue IgG/IgM3.0 Combo Rapid Test commercialized by CTK Biotech, Inc.) or an ELISA (Anti-Dengue IgG ELISA commercialized by Euroimmun) if the RDT result is negative. Only subjects identified as dengue seropositive will be eligible to participate in the study.

It is to be noted that subjects who previously tested negative by RDT for previous exposure to dengue can be re-screened using IgG ELISA.

During the Screening Visit, applicable inclusion and exclusion criteria will be checked and a physical / clinical examination will be performed.

5.2.4 Inclusion Criteria

Consent will be provided once at the Screening Visit. Inclusion criteria will be checked at Screening Visit and again at the first vaccination visit (V01 at D0).

An individual must fulfill all of the following criteria to be eligible for study enrollment:

- 1) Aged 18 to 50 years on the day of first study vaccination (study product administration) ("18 to 50" means from the day of the 18th birthday to the day before the 51th birthday)
- 2) ICF has been signed and dated
- 3) Able to attend all scheduled visits and to comply with all trial procedures
- 4) Documented seropositivity for HIV-1 infection based on the Brazilian HIV Guidelines' laboratory criteria (ie, 2 positive results obtained from different and independent determination methods) or detectable HIV-1 viral load results in the past
- 5) Stable HIV condition according to Brazilian HIV Guidelines (ie, with both CD4 count > 350 cells/mm³ and sustainable and undetectable HIV viral load [< 50 copies/mL]) for at least 1 year before consent
- 6) Stable ART regimen based on local HIV protocol for at least 1 year before consent
- 7) Previous exposure to dengue confirmed by RDT or dengue IgG ELISA

5.2.5 Exclusion Criteria

Exclusion criteria will be checked at Screening Visit and again at the first vaccination visit (V01 at D0). An individual fulfilling *any* of the following criteria is to be excluded from study enrollment:

An individual fulfilling *any* of the following criteria is to be excluded from trial enrollment:

- 1) Subject is pregnant, or lactating, or of childbearing potential (to be considered of non-childbearing potential, a female must be pre-menarche or post-menopausal for at least 1 year,

surgically sterile, or using an effective method of contraception or abstinence from at least 4 weeks prior to the first vaccination until at least 4 weeks after the last vaccination).

- 2) Participation at the time of study enrollment (or in the 4 weeks preceding the first trial vaccination) or planned participation during the present trial period in another clinical trial investigating a vaccine, drug, medical device, or medical procedure.
- 3) Receipt of any vaccine in the 4 weeks preceding the first trial vaccination or planned receipt of any vaccine in the 4 weeks following any trial vaccination.
- 4) Previous vaccination against dengue disease with either the trial vaccine or another vaccine.
- 5) Receipt of immune globulins, blood or blood-derived products in the past 3 months.
- 6) Self-reported or suspected congenital or acquired immunodeficiency, except HIV; or receipt of immunosuppressive therapy such as anti-cancer chemotherapy or radiation therapy within the preceding 6 months; or long-term systemic corticosteroid therapy (prednisone or equivalent for more than 2 consecutive weeks within the past 3 months).
- 7) Previous AIDS, defined as the occurrence of opportunistic infection in the last 2 years before consent.
- 8) Known systemic hypersensitivity to any of the vaccine components, or history of a life-threatening reaction to the vaccines used in the trial or to a vaccine containing any of the same substances.
- 9) Deprived of freedom by an administrative or court order, or in an emergency setting, or hospitalized involuntarily.
- 10) Current alcohol abuse or drug addiction.
- 11) Chronic illness that, in the opinion of the Investigator, is at a stage where it might interfere with trial conduct or completion.
- 12) Moderate or severe acute illness/infection (according to Investigator judgment) or febrile illness (temperature $\geq 38.0^{\circ}\text{C}$) on the day of vaccination. A prospective subject should not be included in the study until the condition has resolved or the febrile event has subsided.
- 13) Identified as an Investigator or employee of the Investigator or study center with direct involvement in the proposed study, or identified as an immediate family member (ie, parent, spouse, natural or adopted child) of the Investigator or employee with direct involvement in the proposed study.
- 14) Previous CD4 count $< 200 \text{ cells/mm}^3$ (nadir) since diagnosis of HIV
- 15) History of chronic and active hepatitis B infection or HBsAg-positive
- 16) History of chronic and active hepatitis C infection or HCV Ab-positive
- 17) Aspartate aminotransferase (AST), alanine aminotransferase (ALT), urea and creatinine > 3 times the upper limit of normal range (ULN)
- 18) Hemoglobin (Hb) $< 10 \text{ g/dL}$
- 19) White blood cell count (WBC) $< 1500 \text{ cells/mm}^3$

20) Platelets < 100 000 cells/mm³

If the subject has a primary physician who is not the Investigator, the site should contact this physician with the subject's consent to inform him / her of the subject's participation in the study. In addition, the site should ask this primary physician to verify exclusion criteria relating to previous therapies, such as receipt of blood products or previous vaccines.

5.2.6 Medical History

Prior to enrollment, subjects will be assessed for pre-existing conditions and illnesses, both past, and ongoing. Any such conditions will be documented in the source document. Significant (clinically relevant) medical history (reported as diagnosis) including conditions/illnesses for which the subject is or has been followed by a physician or conditions/illnesses that could resume during the course of the study or lead to an SAE or to a repetitive outpatient care will be collected in the CRB. The significant medical history section of the CRB contains a core list of body systems and disorders that could be used to prompt comprehensive reporting, as well as space for the reporting of specific conditions and illnesses.

For each condition, the data collected will be limited to:

- Diagnosis (this is preferable to reporting signs and symptoms)
- Presence or absence of the condition at enrollment

The reporting of signs and symptoms in lieu of a diagnosis is strongly discouraged.

Dates, medications, and body systems are not to be recorded, and the information collected will not be coded. Its purpose is to assist in the later interpretation of safety data collected during the study.

5.2.7 Contraindications for Subsequent Vaccinations

The CYD dengue vaccine should not be administered to seronegative persons.

5.2.7.1 Temporary Contraindications

Should a subject experience one of the conditions listed below, the Investigator will postpone further vaccination until the condition is resolved. Postponement must still be within the timeframe for vaccination indicated in the [Table of Study Procedures](#).

- Moderate or severe acute illness/infection (according to Investigator judgment) or febrile illness (temperature $\geq 38.0^{\circ}\text{C}$) or any clinical condition on the day of vaccination, that according to the Investigator's judgment could increase the risk of the subject in case of a new injection (this includes abnormal biological parameters [ie, hematic biometry, biochemistry] performed as per routine management of HIV assessment prior to injection). A subject should not receive a further injection until the condition has resolved or the febrile event has subsided.
- Receipt of any vaccine within the 4 weeks preceding vaccination.
- CD4 count pre-injection ≤ 350 cells/mm³ and/or detectable HIV viral load (≥ 50 copies/mL) based on a second confirmatory test 4 weeks later. A subject should not receive a further

vaccination until the CD4 count is > 350 cells/mm³ and the HIV viral load is undetectable (<50 copies/mL). Time windows for the next vaccination should be respected.

5.2.7.2 Definitive Contraindications

Should a subject experience 1 of the conditions listed below, the Investigator will discontinue vaccination:

- 1) Pregnancy, as indicated by a positive urine test
- 2) Dengvaxia® administered inadvertently during the study (eg, as part of a vaccination campaign)
- 3) An anaphylactic or other significant allergic reaction to the previous dose of vaccine
- 4) Abnormal laboratory parameter of Grade 2 or 3 and assessed by the Investigator as related to the previous dose of vaccine
- 5) Subject deprived of freedom by an administrative or court order, or in an emergency setting, or hospitalized without her/his consent
- 6) Self-reported or suspected congenital or acquired immunodeficiency, except HIV, or receipt of immunosuppressive therapy such as anti-cancer chemotherapy or radiation therapy within the preceding 6 months, or long-term systemic corticosteroids therapy (prednisone or equivalent for more than 2 consecutive weeks within the past 3 months)
- 7) Ongoing clinical AE related to the previous study vaccination, and in the Investigator's opinion, contraindicating further vaccination
- 8) SAE related to the study vaccine following the previous study vaccination
- 9) Confirmed CD4 count < 200 cells/mm³

Subjects will not be withdrawn due to contraindication but will be followed-up for safety. Subjects will not be replaced.

If a female subject who has already received at least one injection becomes pregnant during the study, she will continue to be followed for safety assessments until delivery or until 6 months after the last injection, whichever is the latest. No additional injections will be administered.

Subjects with a definitive contraindication will continue to be followed-up for the study-defined safety and immunogenicity assessments, as applicable.

5.2.8 Conditions for Withdrawal

Subjects will be informed that they have the right to withdraw from the study at any time.

For example, a subject may be withdrawn from the study:

- At the discretion of the Investigator or Sponsor due to safety concerns (withdrawal) or to significant non-compliance with the protocol (based on the Investigator's judgment), without the subject's permission
- At the request of the subject (dropout)

The reason for a withdrawal or dropout should be clearly documented in the source documents and on the CRB.

The Investigator must determine whether voluntary withdrawal is due to safety concerns (in which case, the reason for discontinuation will be noted as “AEs”) or for another reason.

Withdrawn subjects will not be replaced.

5.2.9 Lost to Follow-up Procedures

In the case of subjects who fail to return for a follow-up examination, documented reasonable effort (ie, documented telephone calls and certified mail) should be undertaken to locate or recall them, or at least to determine their health status while fully respecting their rights. These efforts should be documented in the source documents.

5.2.10 Classification of Subjects Who Discontinue the Study

For any subject who discontinues the study prior to completion, the most significant reason for early termination will be checked in the CRB. Reasons are listed below from the most significant to the least significant (refer to the CRF completion instructions for additional details and examples):

Serious Adverse Event	To be used when a subject drops out of or is withdrawn from the study by the Investigator because of the occurrence of an SAE, as defined in Section 9.1.1.1
Adverse Event	To be used when the subject is permanently terminated from the study because of an AE (including an SAE), as defined in Section 9.1.1.1 . This category also applies if the subject experiences a definitive contraindication that is an SAE or AE.
Non Compliance with Protocol	To be used when the Investigator withdraws a subject from the study because of failure to follow the protocol, including when it is retrospectively discovered that a subject did not fulfill the eligibility criteria. The Investigator will provide a comment as to the specific cause of non-compliance.
Lost to Follow-up	To be used when the subject cannot be found or contacted in spite of efforts to locate him/her before the date of his/her planned last visit, as outlined in Section 5.2.9 . The certified letter was sent by the Investigator and returned unsigned, and the subject or parent/guardian did not give any other news and did not come to any following visit.
Protocol Deviation	To be used: 
• In case of significant non-compliance with the protocol (eg, deviation of the Inclusion / Exclusion criteria, non-compliance with time windows, blood sampling, or vaccination refusal, missed injection/treatment, or error in the vaccine/treatment administration)• If the subject experiences a definitive contraindication that is not an SAE or AE• The subject or the parent/guardian signed the certified letter sent by the Investigator but did not give any other news and did not come to any following visit

Withdrawal by Subject To be used:

- When the subject or parent/guardian indicated unwillingness to continue in the study
- When the subject or parent/guardian made the decision to discontinue participation in the study for any personal reason other than an SAE/AE (eg, subject is relocating, inform consent withdrawal, etc.)

5.2.11 Follow-up of Discontinuations

The site should complete all scheduled safety follow-ups and contact any subject who has prematurely terminated the study because of an AE or a protocol deviation.

For subjects where the reason for early termination was lost to follow-up or if the subject withdrew informed consent and specified that they do not want to be contacted again and it is documented in the source document, the site will not attempt to obtain further safety information.

If the subject's status at the end of the study is "Withdrawal by Subject", the site will attempt to contact them for the 6-month follow-up except if they specified that they do not want to be contacted again and it is documented in the source document.

5.2.12 Follow-up and Reporting of Pregnancies

Pregnancy is an exclusion criterion for enrollment in this study, but a subject could potentially become pregnant during her participation. In case of pregnancy during the study and if at least 1 dose of the study vaccine(s) has been administered, the subject will not be discontinued from the study, but no further vaccination will be administered until after delivery (if applicable and still within the study vaccination window). However, the subject will be followed for safety assessment (and may be followed for immunogenicity assessment, if applicable).

All pregnancy cases should be reported if they occurred during the study. To report the pregnancy case, the Investigator must fill out Pregnancy Reporting forms in the electronic data capture (EDC) system and inform the Sponsor within 1 month of identifying a pregnancy case.

If the EDC system is not available, the Investigator must fill out a paper Pregnancy Reporting Form (provided by the Sponsor at the start of the study) and inform the Sponsor within 1 month of identifying a pregnancy case.

Study staff must then maintain contact with the subject to obtain information about the outcome (ie, details about the delivery and the newborn, or about pregnancy termination) and must update the Pregnancy Reporting forms even after the end of the study. This information should be provided to the Sponsor within 1 month of delivery.

Pregnancy itself is not considered an AE, but any complications during pregnancy are to be considered as AEs, and in some cases could be considered SAEs. Spontaneous abortions, blighted ovum, fetal death, stillbirth, and congenital anomalies reported in the baby are always considered as SAEs, and the information should be provided to the Global Pharmacovigilance (GPV) Department regardless of when the SAE occurs (eg, even after the end of the study).

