It is important to note that, if the attempt(s) to collect blood is (are) unsuccessful, the subject should be given the opportunity for another attempt within the Visit window. If a blood sample cannot be obtained, the reason will be recorded in the blood sampling page of the CRF.

- 5) Remind the subject to call the study center if a serious medical event occurs.
- 6) Arrange an appointment for the next visit (V04; at V01 + 28D [+14 days]).
- 7) Complete the relevant CRF pages for this visit.

Visit 4 (Inj 1+28D [+14 days]): Collection of Safety Information and Blood Sample

- 1) Collect DC1 and check the information entered into it by interviewing the subject and request information concerning any medical event, serious, or not, that may have occurred since Visit 3
- 2) Record any AEs and any reportable concomitant medications
- 3) Perform a physical examination and record the subject's axillary temperature (if necessary)
- 4) Obtain a blood sample (see [Section 7.1](#) for detailed instructions regarding the handling of blood samples), record the date of collection

It is important to note that, if the attempt(s) to collect blood is (are) unsuccessful, the subject should be given the opportunity for another attempt within the Visit window. If a blood sample cannot be obtained, the reason will be recorded in the blood sampling page of the CRF.

- 5) Remind the subject to call the study center if a serious medical event occurs
- 6) Provide the subject with DC2 and remind her/him to bring it back when she/he returns for Visit 5
- 7) Arrange an appointment for the next visit (V05; at V01 + 6 months (M6) [\pm 20 days])
- 8) Complete the relevant CRF pages for this visit

Visit 5 (Inj 2 [M6; \pm 20 days]): Collection of safety information and vaccination

- 1) Collect DC2 and check the information entered into it by interviewing the subject and request information concerning any medical event, serious, or not, that may have occurred since last Visit

- 2) Record any reportable concomitant medications
- 3) Perform a physical examination and record the subject's axillary temperature before injection
- 4) Check any contraindication to vaccination
- 5) Check for confirmation of previous exposure to dengue (from PRNT laboratory results)
- 6) Perform a urine pregnancy test for all women enrolled in the study
- 7) The person in charge of injections ("vaccinator") or authorized designee contacts the IRT to obtain the assigned product to be administered

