Note: A follow-up visit can be arranged depending on the information provided during the phone call, at the Investigator's discretion.

Visit 6 (Inj 2+28D [+14 days]): Collection of Safety Information and Blood Sample

- 1) Collect DC3 and check the information entered into it by interviewing the subject and request information concerning any medical event, serious, or not, that may have occurred since Visit 5
- 2) Record any AEs and any reportable concomitant medications
- 3) Perform a physical examination and record the subject's axillary temperature (if necessary)
- 4) Remind the subject to call the study center if a serious medical event occurs
- 5) Obtain a blood sample (see [Section 7.1](#) for detailed instructions regarding the handling of blood samples), record the date of collection

It is important to note that, if the attempt(s) to collect blood is (are) unsuccessful, the subject should be given the opportunity for another attempt within the Visit window. If a blood sample cannot be obtained, the reason will be recorded in the blood sampling page of the CRF.

- 6) Provide the subject with DC4 and remind her/him to bring it back when she/he returns for Visit 7
- 7) Arrange an appointment for the next visit (V07; at V01 + 12 months (M12) [\pm 20 days])
- 8) Complete the relevant CRF pages for this visit

Visit 7 (Inj 3 [M12; \pm 20 days]): Collection of safety information and vaccination

Same procedure as for Visit 5. Subject is provided with DC5.

Phone Call 3 (Inj 3+7D [+3 days]): Safety Follow-up Phone Call

Same procedures as for Phone Call 1.

Phone Call 4 (Inj 3+14D [+3 days]): Safety Follow-up Phone Call

Same procedures as for Phone Call 2.

Visit 8 (Inj 3+28D [+14 days]): Collection of Safety Information and Blood Sample

- 1) Collect DC5 and check the information entered into it by interviewing the subject and request information concerning any medical event, serious, or not, that may have occurred since Visit 7
- 2) Record any AEs and any reportable concomitant medications
- 3) Perform a physical examination and record the subject's axillary temperature (if necessary)
- 4) Obtain a blood sample (see [Section 7.1](#) for detailed instructions regarding the handling of blood samples), record the date of collection

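### Protocol 5.2.12 lets dosing resume after delivery, while 5.2.7.2 bars any further injection once a subject becomes pregnant

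*Protocol*

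**What the plan says.** Two sections of the protocol set the dosing rule for a subject who becomes pregnant after at least one injection.

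- **Section 5.2.7.2 (Definitive Contraindications).** The first item is "Pregnancy, as indicated by a positive urine test", and any item on that list requires the investigator to stop vaccination. A later paragraph on women who become pregnant on study provides for continued safety follow-up and adds: "No additional injections will be administered". It makes no exception for the period after delivery.
- **Section 5.2.12 (Follow-up and Reporting of Pregnancies).** The woman stays in the study, but "no further vaccination will be administered until after delivery (if applicable and still within the study vaccination window".

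Lactation is dealt with only at entry. Exclusion criterion 1 in Section 5.2.5 begins "Subject is pregnant, or lactating, or of childbearing potential", and the section states: "Exclusion criteria will be checked at Screening Visit and again at the first vaccination visit". Before Injection 2, the Visit 5 procedures in Section 5.1.4 include a urine pregnancy test and the step "Check any contraindication to vaccination". For Visit 7 (Injection 3) they say "Same procedure as for Visit 5. Subject is provided with DC5". Lactation is on neither the temporary list (5.2.7.1) nor the definitive list (5.2.7.2).

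The SAP sets no dosing rule here. Its Section 4.4.1.5.1 only says that pregnancy information is listed and not analysed.

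**The concern.** The sections give different instructions for the same woman. One ends her vaccination; the other suspends it and allows it to resume. Neither cross-refers to the other or says which governs. Staff handling a pregnancy would naturally turn to 5.2.12, the section named for it, and would read there that dosing may restart.

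Subject safety is what is at stake. The clause in 5.2.12 is a written route to giving a live attenuated vaccine, or placebo, to a woman whom 5.2.7.2 bars and who, if breastfeeding, could not have been enrolled. At Visits 5 and 7 only two things would stop that dose: 5.2.7.2 itself, if it is applied, and the 5.2.7.1 item that lets the investigator postpone for a condition raising the risk to the subject. That item speaks of the subject, not of a breastfed infant.

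**Working it through.** The plan gives no figure to reproduce. The check has two parts.

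**1. The two rules side by side**

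| | 5.2.7.2 | 5.2.12 |
|---|---|---|
| Trigger | Pregnancy after at least one injection | Pregnancy after at least one dose |
| Stays in follow-up | Yes | Yes |
| Injection after delivery | Never | Allowed if applicable and in window |

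The trigger is the same and the last row differs. Never re-dosing satisfies both sections; re-dosing after delivery satisfies only 5.2.12.

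**2. Can a delivery fall before a remaining window closes?**

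Inputs from the protocol: injections at D0, M6 and M12, with ±20 days for Injections 2 and 3 (Table of Study Procedures).

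Assumptions not in the documents: M6 = day 183 and M12 = day 365, counted from Injection 1; conception on or after day 0; *g* days from conception to delivery, with *g* = 238, 266 or 280.

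Windows:
- Injection 2: 183 ± 20 = days 163 to 203
- Injection 3: 365 ± 20 = days 345 to 385

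Injection 2 after delivery needs *g* ≤ 203. None of the three values qualifies.

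Injection 3 after delivery needs conception by day 385 − *g*. The same number is the longest possible time from delivery to Injection 3 (conception on day 0, dose on day 385).

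| *g* (days) | 385 − *g* |
|---|---|
| 238 | 147 |
| 266 | 119 |
| 280 | 105 |

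Could she have received Injection 2 before conceiving? The earliest Injection 2 is day 163, so this needs 163 + *g* ≤ 385, or *g* ≤ 222. Again none of the three values qualifies, so in this scenario Injection 2 has been missed.

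Gap between doses:
- Planned, Injection 2 to Injection 3: 345 − 203 = 142 to 385 − 163 = 222 days
- With Injection 2 missed, Injection 1 to Injection 3: 345 to 385 days

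**Sensitivity to a missed early pregnancy.** Suppose a urine test can miss the first 14 days (assumed), at Visit 1 as well as later.
- Injection 2 after delivery: *g* ≤ 203 + 14 = 217
- Injection 2 before detection, then Injection 3 after delivery: *g* ≤ 222 + 14 = 236
- Longest delivery-to-dose times: 147 + 14 = 161, 119 + 14 = 133 and 105 + 14 = 119 days

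Both limits stay below 238, so for *g* from 238 to 280 the only possible post-delivery dose is still Injection 3.

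**The case against.** The strongest reply is that 5.2.12 concerns follow-up and reporting, and that its clause is doubly conditional. The dosing decision at Visits 5 and 7 goes through the contraindication check, which leads to 5.2.7, where pregnancy is definitive. On that view the words on applicability make the clause subject to 5.2.7.2, and harm needs a site to skip a prescribed check. It is true that 5.2.7.2 stops the dose when applied. But if 5.2.7.2 always governs, the clause never has any effect and should go; if it has effect, it contradicts 5.2.7.2. The check is also less secure than it looks: the listed item is worded around a positive urine test, and by Visit 7 a woman who has delivered may test negative.

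A second reply is that the scenario assumes a subject who misses Injection 2 may still receive Injection 3. The protocol nowhere says so, and Section 6.1.1.3 describes three doses at 6-month intervals. Section 5.2.10 also gives a missed injection as an example of a protocol deviation leading to early termination. This assumption has to be stated. Nothing expressly forbids Injection 3 after a missed Injection 2, however, and both 5.2.7.2 and 5.2.12 keep the woman in the study.

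Third, lactation at that visit needs a chain of events: pregnancy despite a criterion requiring a woman otherwise of childbearing potential to be "using an effective method of contraception or abstinence", conception early enough, reliance on 5.2.12, and breastfeeding at that time. That limits how often it could happen. It does not remove the conflict in the text.

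**Conclusion.** The inconsistency is real and minor. For a woman pregnant after at least one dose, 5.2.12 permits what 5.2.7.2 forbids. With 238 to 280 days from conception to delivery, the permitted dose could only be Injection 3, given that it may follow a missed Injection 2. It would be within its own M12 window but about a year after her only earlier dose. Only a markedly shorter pregnancy would bring Injection 2 into play.

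The documents give no number of women or pregnancies and no estimate of harm from dosing a lactating woman, so neither is claimed; few subjects would be affected. No analysis-set definition and no descriptive conclusion changes. It is a point to consider, on safety grounds alone.

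**What to change.** In Section 5.2.12, delete the clause that defers vaccination until after delivery, together with its bracketed condition, and write instead: *and she will receive no further injections (see Section 5.2.7.2)*. This follows the stricter rule and also closes the lactation route for a woman who delivers on study.

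If the sponsor does intend dosing after delivery, the alternative is to amend 5.2.7.2 to allow it and to add lactation to the contraindications checked before Injections 2 and 3.

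The preferred change replaces one clause and alters no visit, sample size, analysis set or SAP text. Because it bears on subject safety, Section 5.4 would probably class it as a substantial amendment needing IEC/IRB approval and submission to the regulatory authorities; it could be combined with another amendment.
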